## 6.5 Observation period

### [1] Xeljanz group:

- (1) Registered subjects up to a certain sample size exceeding 3000 subjects from the start of registration: 3 years (36 months) from the date of treatment start
- (2) Registered subjects after the above (1): Only 6 months from the date of treatment start

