## Appendix

### “3. Target sample size”

A list of combinations for “certain sample size” in the Xeljanz and control groups

Sample size for safety analysis in “3. Target sample size” g)			
“Certain sample size h) that requires 3-year observation		6-month observation	
(1) Sample size in the control group	(2) Sample size in the Xeljanz group	(3) Sample size in the Xeljanz group	(4) Sample size in the Xeljanz group Total [(2)+(3)]
2000	4000	0	4000
2050	3814	186	4000
2100	3653	347	4000
2150	3511	489	4000
2200	3385	615	4000
2250	3273	727	4000
2300	3173	827	4000
2350	3082	918	4000
2400	3000	1000	4000

g) Subjects who meet the conditions described in “2. Subjects”.

h) A “certain sample size” will be reached when both the sample size in the control group and the sample size in the Xeljanz group exceed the number of subjects in any line of the combination of (1) and (2).

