#### **5. ANALYSIS SETS**

##### **5.1. Safety Analysis Set**

###### **5.1.1. Safety analysis of the Xeljanz group**

- Safety analysis set

Of the enrolled patients with a scheduled observation period of 3 years and 6 months, those who have been confirmed to have received Xeljanz at least once are included. However, the following patients will be excluded from the safety analysis set.

- a. No CRF was collected (description in the report: "CRF not collected");
  - b. There was a violation or flaw of the contract (description in the report: "Violation/flaw of contract");
  - c. There was a violation in the enrollment process (description in the report: "Enrollment violation");
  - d. No information on the administration of survey drug was reported (description in the report: "No administration information");
  - e. No information on adverse events was reported (ie., existence or non-existence of adverse events is unidentifiable) - No visits after the initial prescription (description in the report: "No information on adverse events - No re-visits");
  - f. No information on adverse events was reported - Visits conducted after the initial prescription, but no record (description in the report: "No information on adverse events - No record").
- MTX adherent safety analysis set

The MTX adherent safety analysis set is defined as the patients with rheumatoid arthritis who have been poorly controlled if methotrexate (MTX) at a dose of more than 8 mg/week is continuously used for 3 months or longer among the new patients of the safety analysis set, that is described in the "Guidelines for the use of tofacitinib for all patients post-marketing surveillance".

The new patient is defined as the patients in which administration of Xeljanz was started for the first time after the registration of this surveillance in the Xeljanz group. In addition, the target patients with rheumatoid arthritis are 16 years old or older, and patients under 16 years old are excluded.

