### **5.1.2. Comparison of the Xeljanz group and the control group**

- Comparative analysis set

Of the enrolled patients with a scheduled observation period of 3 years, those who were confirmed to treat Xeljanz in the Xeljanz group and a control drug (control drug is MTX, biological agents, DMARDs or immunosuppressive drug) at least once were included in the control group. The patients who apply to a to f in Section 5.1.1 are excluded.

The control group also excludes patients who do not meet the MTX criteria and patients who have been treated with Xeljanz.

- MTX adherent comparative analysis set

The MTX adherent comparative analysis set of the Xeljanz group is the patients who meets the MTX criteria among the new patients of the comparative analysis set.

As for the control group, since the comparative analysis set of the control group is limited to the patients who meet the MTX criteria, the same set is also used as the control group of MTX adherent comparative analysis set.

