#### **8.2.3.2. Safety analysis in the Xeljanz group**

Statistical analyses in this section will be performed in the safety analysis set in the Xeljanz group. Adverse drug reactions and adverse events will be analyzed for all those reactions or events that developed during the survey period, and those that developed by 6 months after the start of Xeljanz.

- Development of adverse drug reactions**

The number of patients with adverse drug reactions and the incidence proportion will be calculated for each SOC and PT.

The number of patients with adverse drug reactions and the incidence proportion will also be calculated for each SOC and PT for new patients in whom treatment started from this survey, patients who participated in clinical trials, and patients administered Xeljanz at other institutions. Furthermore, the calculation will also be performed for the subpopulations that do and do not meet the MTX criteria in the Xeljanz group.

- Development of serious adverse drug reactions**

The number of patients with serious adverse drug reactions and the incidence proportion will be calculated for each SOC and PT.

The number of patients with serious adverse drug reactions and the incidence proportion will also be calculated for each SOC and PT for new patients in whom treatment started from this survey, patients who participated in clinical trials, and patients administered Xeljanz at other institutions. Furthermore, the calculation will also be performed for the subpopulations that do and do not meet the MTX criteria in the Xeljanz group.

- **Development of serious adverse events**

The number of patients with serious adverse events and the incidence proportion will be calculated for each SOC and PT.

- **Development of adverse events**

The number of patients with adverse events and the incidence proportion will be calculated for each SOC and PT.

- **Development of adverse drug reactions in patients included in and excluded from the safety analysis set**

The number of patients with adverse drug reactions among patients for whom the CRF is collected and who are included in and excluded from the safety analysis set and the incidence proportion will be calculated for each SOC and PT.

- **Details of adverse drug reactions by event**

The number of patients with adverse drug reactions and the incidence proportion will be calculated for each SOC and PT for each category in Table 8.

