**Table 8. Tabulation Items Concerning the Details of Adverse Drug Reactions by Event**

Item	Category	Order of precedence
Seriousness	Serious, non-serious	Serious → non-serious
Known/unknown	Known, unknown	Unknown → known
Outcome	Resolved/recovered, recovering, recovered with sequel, not recovered, unknown	An event that last developed
Number of days to onset	Start of treatment - 1 month (Day 1 to Day 31), 1 month< - 3 months (Day 32 to Day 92), 3 months< - 6 months (Day 93 to Day 184), 6 months< - 9 months (Day 185 to Day 275), 9 months< - 12 months (Day 276 to Day 366), 12 months< - 18 months (Day 367 to Day 549), 18 months< - 24 months (Day 550 to Day 731), 24 months< - 30 months (Day 732 to Day 914), 30 months< - 36 months (Day 914 to Day 1096), >36 months (Day 1097-)	An event that first developed
Change in administration of Xeljanz	No change, dose reduction, temporary suspension, discontinuation	Discontinuation → temporary suspension → dose reduction → no change

• **Subgroup analysis**

The number and proportion of patients with at least 1 following each adverse drug reaction will be tabulated for each factor specified in [Section 5.4](#) in accordance with [Section 8.1.3](#). Tests will be performed between the levels of each background factor.

- Serious infections;
- Neutrophil count decreased and neutropenia;
- Lymphocyte count decreased and lymphopenia;
- Hemoglobin decreased and anemia;
- Lipid increased and hyperlipidemia;
- Malignant tumors (including lymphoma);
- Gastrointestinal perforation;
- Cardiovascular adverse events;
- Hepatic dysfunction;
- Interstitial pneumonia;
- Herpes Zoster.

The following tabulation and analysis will be performed for sex, age class and each subgroup in patients with and without hepatic dysfunction and patients with and without renal dysfunction:

- Development of adverse drug reactions;
- Development of serious adverse drug reactions;
- Development of serious adverse events.

A list of adverse reactions for contraindicated patients are created. Furthermore, if necessary, the number of patient with adverse reactions and their proportions are calculated for each SOC and PT.

- **Key survey items**

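### Whole-survey adverse-reaction proportions and factor-level tests in the Xeljanz group pool patients scheduled for 3 years with later patients scheduled for 6 months, without allowing for time at risk

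*SAP*

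**What the plan says.** Protocol 6.5 sets two follow-up lengths in the Xeljanz group. Patients registered first are observed for "3 years (36 months) from the date of treatment start". For the rest the rule is "Registered subjects after the above (1): Only 6 months from the date of treatment start". The protocol Appendix lets the second cohort range from 0 to 1000 of the 4000 target patients; its last row reads "2400 3000 1000 4000" (control, Xeljanz 3-year, Xeljanz 6-month, Xeljanz total).

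SAP 5.1.1 builds the Xeljanz safety set from both cohorts: "Of the enrolled patients with a scheduled observation period of 3 years and 6 months". SAP 8.2.3.2 then says "Statistical analyses in this section will be performed in the safety analysis set in the Xeljanz group", and "Adverse drug reactions and adverse events will be analyzed for all those reactions or events that developed during the survey period". That sentence continues by requiring the same analyses for events in the first 6 months of Xeljanz.

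The measure for reactions by SOC and PT is the incidence proportion. SAP 8.1.5 defines it as patients with the event over number of patients. For eleven listed reactions the subgroup paragraph tabulates proportions by background factor and adds "Tests will be performed between the levels of each background factor". SAP 8.1.3 makes these Fisher's exact test for nominal factors and the exact Cochran-Armitage test for ordinal ones.

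The comparative set in SAP 5.1.2 is defined differently: "Of the enrolled patients with a scheduled observation period of 3 years, those who were confirmed" to have been treated. The 6-month cohort is therefore left out of the comparison with the control group.

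**The concern.** A crude proportion has a clear meaning only when everyone is watched for about the same time. Here up to a quarter of the target patients are scheduled for one sixth of the follow-up of the others. The pooled whole-survey proportion is then neither a 6-month nor a 3-year risk, and its value depends on how many patients fell into each cohort.

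The tests raise a further problem. Cohort membership follows registration order, so any background factor whose frequency drifted over the registration period is linked to length of observation. A factor more common among late registrants will look protective, and one more common among early registrants will look harmful, with no true effect. Real associations can be hidden in the same way. Factors affecting safety and long-term safety are both stated objectives (Protocol 1), so these tables will be read.

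**Working it through.** **Inputs from the documents.** Malignant tumor rate 1.16 per 100 person-years, drop-out about 50% at 3 years, 104 expected events in 4000 patients (Protocol 3, rationale). Cohort sizes from the Protocol Appendix. Two-sided 5% tests (SAP 4).

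**Reproducing the plan's figure.** With linear drop-out, mean follow-up over 3 years is 3 × (1 + 0.5)/2 = 2.25 years. Then 4000 × 2.25 = 9000 person-years, and 0.0116 × 9000 = 104.4, which matches 104. Exponential drop-out gives 100.4 and no drop-out 139.2, so linear drop-out is used below.

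**Time at risk by cohort.** On the same line, 1 − 0.5/6 = 0.917 of patients remain at 6 months. Mean time is 0.5 × (1 + 0.917)/2 = 0.479 years. The ratio is 2.25/0.479 = 4.7.

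**Observed proportion by cohort.** With constant hazard h, the observed proportion is the integral of h·exp(−ht)·(1 − t/6) from 0 to 3, or from 0 to 0.5. At h = 0.0116 this gives 2.57% and 0.55%.

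**Pooled proportion by Appendix row.** The formula is (n3 × 2.57% + n6 × 0.55%)/4000; results are from unrounded values.

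| 3-year + 6-month | Pooled | Below 3-year cohort |
|---|---|---|
| 4000 + 0 | 2.57% | 0% |
| 3653 + 347 | 2.40% | 6.8% |
| 3385 + 615 | 2.26% | 12.1% |
| 3173 + 827 | 2.15% | 16.2% |
| 3000 + 1000 | 2.07% | 19.6% |

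At assumed rates of 5 and 10 per 100 person-years the last row gives 19.4% and 19.1%. A rate is not affected: at 3000 + 1000 there are 3000 × 2.25 + 1000 × 0.479 = 7229 person-years and 83.9 events, still 1.16 per 100.

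**Factor comparisons with no true effect, 3000 + 1000.** The splits are assumptions; the documents give none.

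- Factor present in 20% of 3-year and 40% of 6-month patients. Factor-positive patients are 600 + 400 (40% short follow-up) and factor-negative 2400 + 600 (20%). Risk ratio = (0.6 × 2.57 + 0.4 × 0.55)/(0.8 × 2.57 + 0.2 × 0.55) = 1.76/2.17 = 0.81. Simulated Fisher tests reject in about 10% of runs.
- Two levels of 2000 patients, with 20% and 30% short follow-up: risk ratio 2.17/1.96 = 1.10.
- Two levels of 2000, with 15% and 35%: risk ratio 2.27/1.87 = about 1.2.

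Rejection by Fisher's test in 3000 simulated runs, two levels of 2000, no true effect:

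| Short follow-up in the two levels | 1.16/100 PY | 5/100 PY (assumed) | 10/100 PY (assumed) |
|---|---|---|---|
| 25% / 25% | 3.5% | 5.0% | 4.2% |
| 20% / 30% | 4.8% | 14.0% | 23.4% |
| 15% / 35% | 11.8% | 43.6% | 71.7% |

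Restricted to events in the first 6 months, the same test rejects in 2.7% to 4.6% of runs.

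**Does restriction to the 3-year cohort suffice?** True 3-year risk at this rate is 1 − exp(−0.0348) = 3.42%. The cohort's crude proportion of 2.57% is already 25% below that because of drop-out.

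**The case against.** The strongest reply is that the plan already holds most of the remedy. The 6-month analysis covers everything in SAP 8.2.3.2, including the subgroup tests, and its scheduled window is common to both cohorts. It is also the 6-month data on the 4000 patients that go to the regulator (Protocol 5 and 8.3). Incidence rates are planned for listed events, overall and by time period (SAP 8.2.3.2, key survey items), and for all key items in the MTX adherent and non-adherent sets. Table 8 splits reactions by time to onset. Malignancy and serious infection are compared with control in the 3-year cohort using rates, single-factor incidence, Kaplan-Meier and Cox models (SAP 8.2.3.1.1 and 8.2.3.1.2). SAP 4 calls the tests exploratory.

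All of this stands and limits the scope. A reader might infer that the safety plan as a whole ignores time at risk, or that the comparison with control is distorted; the sections just listed show otherwise. A reader might also infer that spurious risk factors are to be expected. The documents do not show that any factor drifted with registration, and if 6-month patients fall equally across factor levels the tests keep their size.

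What does not follow is that the whole-survey results are sound. The 6-month window cannot speak to late events. The key-item rates are not broken down by background factor, so most of the eleven tested reactions have no visible factor comparison that uses time at risk. Exploratory status does not remove bias. Redacted text may hold further time-based analyses; this point rests only on what is visible.

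**Conclusion.** The point holds for two outputs: whole-survey incidence proportions in SAP 8.2.3.2 and whole-survey Fisher or Cochran-Armitage comparisons between factor levels.

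For malignancy the dilution is 0% to about 20% relative to the 3-year cohort. The upper end belongs to the extreme Appendix row, and the final cohort size is not in the documents. Patients outside the MTX criteria are not counted in those rows, so their share is unknown.

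For the tests, the assumed uneven splits give null risk ratios of about 0.8 to 1.2. Excess false positives are modest at the malignancy rate (up to about 12% in the cases shown) and large only for commoner reactions with clearly uneven splits. With equal splits only the proportions are diluted.

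The figures assume constant hazard and linear drop-out; reactions that cluster early would be diluted less. It would be too strong to say that restriction to the 3-year cohort recovers 3-year risk, since that cohort's crude proportion is itself lowered by drop-out.

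**What to change.** In SAP 8.2.3.2:

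1. Name the already planned 6-month window as the primary basis for factor-level tests of proportions in the pooled safety set.
2. For the whole survey period, replace the Fisher and Cochran-Armitage comparisons with rate ratios per patient-year or Cox models.
3. Report whole-survey proportions separately for the 3-year and 6-month cohorts, each beside its person-years and incidence rate, or give Kaplan-Meier estimates.

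The exposure formulae are already in SAP 8.1.5 and the Cox model in 8.1.4. The cost is SAP wording and some extra tables, with no new data.

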**Table 8. Tabulation Items Concerning the Details of Adverse Drug Reactions by Event**

Item	Category	Order of precedence
Seriousness	Serious, non-serious	Serious → non-serious
Known/unknown	Known, unknown	Unknown → known
Outcome	Resolved/recovered, recovering, recovered with sequel, not recovered, unknown	An event that last developed
Number of days to onset	Start of treatment - 1 month (Day 1 to Day 31), 1 month< - 3 months (Day 32 to Day 92), 3 months< - 6 months (Day 93 to Day 184), 6 months< - 9 months (Day 185 to Day 275), 9 months< - 12 months (Day 276 to Day 366), 12 months< - 18 months (Day 367 to Day 549), 18 months< - 24 months (Day 550 to Day 731), 24 months< - 30 months (Day 732 to Day 914), 30 months< - 36 months (Day 914 to Day 1096), >36 months (Day 1097-)	An event that first developed
Change in administration of Xeljanz	No change, dose reduction, temporary suspension, discontinuation	Discontinuation → temporary suspension → dose reduction → no change

• **Subgroup analysis**

The number and proportion of patients with at least 1 following each adverse drug reaction will be tabulated for each factor specified in [Section 5.4](#) in accordance with [Section 8.1.3](#). Tests will be performed between the levels of each background factor.

- Serious infections;
- Neutrophil count decreased and neutropenia;
- Lymphocyte count decreased and lymphopenia;
- Hemoglobin decreased and anemia;
- Lipid increased and hyperlipidemia;
- Malignant tumors (including lymphoma);
- Gastrointestinal perforation;
- Cardiovascular adverse events;
- Hepatic dysfunction;
- Interstitial pneumonia;
- Herpes Zoster.

The following tabulation and analysis will be performed for sex, age class and each subgroup in patients with and without hepatic dysfunction and patients with and without renal dysfunction:

- Development of adverse drug reactions;
- Development of serious adverse drug reactions;
- Development of serious adverse events.

A list of adverse reactions for contraindicated patients are created. Furthermore, if necessary, the number of patient with adverse reactions and their proportions are calculated for each SOC and PT.

- **Key survey items**

**Table 9. Catedories of time period for analysis by time period in key survey items**

Item	Category	Order of precedence
Number of days to onset	Start of treatment - 1 month (Day 1 to Day 31), 1 month< - 3 months (Day 32 to Day 92), 3 months< - 6 months (Day 93 to Day 184), 6 months< - 9 months (Day 185 to Day 275), 9 months< - 12 months (Day 276 to Day 366), 12 months< - 18 months (Day 367 to Day 549), 18 months< - 24 months (Day 550 to Day 731), 24 months< -30 months (Day 732 to Day 914), 30 months< -36 months (Day 914 to Day 1096), >36 months (Day 1097-)	An event that first developed
Number of days to onset (cumulative)	Start of treatment - 1 month (Day 1 to Day 31), Start of treatment - 3 months (Day 1 to Day 92), Start of treatment - 6 months (Day 1 to Day 184), Start of treatment - 9 months (Day 1 to Day 275), Start of treatment - 12 months (Day 1 to Day 366), Start of treatment - 18 months (Day 1 to Day 549), Start of treatment - 24 months (Day 1 to Day 731), Start of treatment -30 months (Day 1 to Day 914), Start of treatment -36 months (Day 1 to Day 1096), Overall period	An event that first developed

- Key survey items for MTX adherent safety analysis set and non MTX adherent safety analysis set.**

For MTX adherent safety analysis set and non MTX adherent safety analysis set , adverse drug reactions and adverse events applicable to key survey item ([Section 6.1](#)) will be tabulated, in accordance with [Section 8.1.5](#), for the number of patients, the frequency and its 95% confidence interval, duration of exposure, and the incidence and its 95% confidence interval. Also, herpes zoster, opportunistic infection, and tuberculosis will be calculated as an individual event.

CCI

#### 8.2.4. Efficacy Analysis

Analysis is performed for each of the MTX adherent efficacy analysis set and the efficacy analysis set. The main analysis target set is the MTX adherent efficacy analysis set.

##### 8.2.4.1. SDAI and CDAI

- **Changes in SDAI and CDAI**

Summary statistics for the measurement of SDAI at each time point and the change from the initiation of administration of Xeljanz will be calculated. For the change, 95% confidence intervals will be calculated.

As for each time point, “Appendix 11.1.1 Definition of Visit Timing” will be followed.

The calculation will be performed for CDAI in the same manner.

Furthermore, summary statistics of measurements, the change will be calculated at each time point up to Month 6 will be calculated with imputation by LOCF (Section 7) for missin data (ie, no data within the acceptable window for a visit in Appendix 11.1.1).

The subgroup analyses by the dose below will be calculated for the aboube analyses.

- Average actual daily dose (<7.5mg,  $\geq 7.5$  mg)
- **Disease activity of SDAI and CDAI**

The proportion of remission and disease activity at each time point for SDAI and the 95% confidence interval for the proportion of remission will be calculated.

As for each time point, “Appendix 11.1.1 Definition of Visit Timing” will be followed.

The calculation will be performed for CDAI in the same manner.

Also, the values with LOCF for "changes in SDAI and CDAI" as described above will be used to calculate the remission at each time point up to Month 6, as well as the proportion of patients in remission and disease activity, as well as a 95% confidence interval for the proportion of patients in remission.

The subgroup analyses by the average actual daily dose will be calculated for the aboube analyses.

Criteria for the assessment of the remission and disease activity of SDAI and CDAI will be based on Table 10.

**Table 10. Criteria for the Assessment of the Disease Activity of SDAI and CDAI**

Evaluation index	Remission	Low disease activity	Moderate disease activity	High disease activity
SDAI	$\leq 3.3$	>3.3 to $\leq 11$	>11 to $\leq 26$	>26
CDAI	$\leq 2.8$	>2.8 to $\leq 10$	>10 to $\leq 22$	>22

#### **8.2.4.2. DAS28**

- Changes in DAS28**

Summary statistics for the measurement of DAS28(4/ESR) at each time point and the change from the initiation of administration of Xeljanz will be calculated. For the change, 95% confidence intervals will be calculated.

As for each time point, “Appendix [11.1.1 Definition of Visit Timing](#)” will be followed.

Furthermore, summary statistics of measurements, the change will be calculated at each time point up to Month 6 will be calculated with imputation by LOCF ([Section 7](#)) for missin data (ie, no data within the acceptable window for a visit in Appendix [11.1.1](#))

The subgroup analyses by the average actual daily dose will be calculated for the abouve analyses.

- Disease activity of DAS28**

The proportion of remission and disease activity at each time point for DAS28(4/ESR) and the 95% confidence interval for the proportion of remission will be calculated.

As for each time point, “Appendix [11.1.1 Definition of Visit Timing](#)” will be followed.

Also, the values with LOCF for "changes in DAS28" as described above should be used to calculate the remission at each assessment timepoint up to Month 6 of treatment, as well as the proportion of patients in remission and disease activity, as well as a 95% confidence interval for the proportion of patients in remission.

The subgroup analyses by the average actual daily dose will be calculated for the abouve analyses.

Criteria for the assessment of the remission and disease activity of DAS28(4/ESR) will be based on Table 11.

